#### DATA AND SAFETY MONITORING PLAN

The treatment interventions and assessment protocols are well-established and pose primarily low risks to subjects. The DSMP focuses on close monitoring by the PI in conjunction with the study MDs. Excessive adverse events and/or any serious events (should they occur) will be reported promptly to the NIH and to the Yale Human Investigation Committee.

A Data and Safety Monitoring Board (DSMB) will monitor this project. This board is already in place at Yale for HIC 2000021769. The DSMB is composed of Yale investigators who are independent of the proposed trial and experienced in various aspects relevant to the current proposal including: conduct of clinical trials, biostatistics, primary care, and the clinical management of obesity and BED.

We have developed a standard DSMB report form that summarizes, *on a twice-yearly basis*:

1. Recruitment, retention, and follow-up rates for the study and compares them to target rates.
2. Rates of data completeness and availability of primary outcome data
3. Occurrence of AEs and SAEs
4. Report of study progress since the last report.
5. Rates of recruitment of women and minorities with respect to targets.

These reports are generated by the study coordinator, and reviewed and signed by the PI prior to their submission to the DSMB. DSMB comments are documented and forwarded to the Yale IRB at the time of the annual review and re-approval. They will also be summarized as part of the annual progress report to NIDDK. However, if adverse events occur in greater magnitude or frequency than expected these will be reported to the DSMB, HIC, and NIH prior to scheduled reports. The Principal Investigator will assume full responsibility for reporting serious and non-serious and unanticipated adverse events. The DSMB may call an ad-hoc meeting to address emergent safety concerns.

Because the projected effect sizes may not be large enough for detection during interim analyses, we are not proposing a preliminary analysis of accumulating efficacy and safety data by treatment assignment. Instead, we propose to submit a twice-yearly report of aggregate data to the DSMB members that contains screening data, baseline demographics, retention data, serious adverse events data, as well as

accrual status, and any other data that will help in the assessment of the clinical trial. Based on this report, each DSMB member will complete a form making one of two recommendations: 1) continue recruitment as planned; or 2) schedule formal DSMB meeting immediately. If any DSMB member recommends a meeting, this will be scheduled, minutes will be kept, the report will be reviewed with the PI, and the committee will vote on whether the study should: 1) continue recruitment unchanged; 2) continue with a protocol amendment; 3) stop recruiting pending further investigation; and 4) the Yale IRB will be informed.

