**Measurement and reporting of adverse events.**

Adverse event data will be collected on an on-going basis. These data will be collected and examined with blindness to the medication conditions. Adverse events data will be reviewed by the PI, co-investigators, and the safety officer throughout this trial (see Table below). A summary of adverse events will be provided to the Yale IRB yearly during the annual renewal review process. Any serious or unanticipated adverse events will be reported to the NIH and to the Yale IRB within 48 hours.

The frequency of data review is summarized in the following table:

Table	Data type	Frequency of Review by PIs and Research Team	Frequency of Review by PI and DSMB
Table 1	Subject accrual	Monthly	Twice Yearly
Table 2	Treatment completion rates (retention/attrition)	Twice Yearly	Twice Yearly
Table 3	Adverse and serious adverse event rates	Twice Yearly	Twice Yearly
Table 4	Checklist for DSMB	NA	Twice Yearly

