Participation rates (retention and attrition) will be reviewed on an ongoing basis by the PIs and co-investigators to identify any potential problems, and formally by the PIs and DSMB twice-yearly. Any differential dropout across blinded study groups and/or higher than expected dropout will be reviewed by the investigators to determine whether any problems are present and what, if any, corrective action needs to be taken.

During the reviews, if the DSMB has concerns about whether attrition has reached a level that might inhibit the ability of the study to address its primary aims, they will suggest a meeting to discuss methods for improving subject retention. Previous pharmacotherapy studies for BED (with comparable time frames for pharmacotherapy) have reported attrition rates between 20% and 38%. Studies of NB for obesity treatment reported attrition of 30% to 45%. Thus, "trigger points" for review and discussion by principal investigator and research staff will be: 35% ("low alert"), 40% ("mid alert"), 45% ("high alert"), 50% ("extreme alert"). With early alerts to problems, action would be taken to avoid higher level alerts; if a higher level alert should arise, more drastic actions would be taken.

Trial Stopping Rules

Given that this study is deemed greater than minimal risk to human subjects, it is more likely that attrition or difficulty in recruiting adequate numbers of participants will require stopping the trial than would excess adverse events. However, as outlined, adverse events will be monitored in all participants, and the safety officer, together with the PI, will alert the Yale IRB and the NIH if a larger (or more serious) than reasonably expected adverse event rate should occur. Other potential issues relating to stopping rules for this trial include:

1. New Information

It is unlikely that any new information will become available during this trial that would necessitate stopping the trial. If new safety data (i.e., pertaining to short-term use of the study medication) become available, this will be evaluated.

2. Limits of Assumptions

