### 3. Limits of Rules

There are other situations that could occur that might warrant stopping the trial and/or including a section on the safety report entitled “Other situations that have occurred since the last safety report that warrant discussion” to allow for communication of concerns.

Finally, as currently outlined above, the DSMB has the authority to stop the trial following any serious adverse event or following reviews of adverse events.

d. For multi-site studies for which the Yale PI serves as the lead investigator: NA

1. How will adverse events and unanticipated problems involving risks to subjects or others be reported, reviewed and managed? *Write here*
2. What provisions are in place for management of interim results? *Write here*
3. What will the multi-site process be for protocol modifications? *Write here*

13. **Statistical Considerations:** Describe the statistical analyses that support the study design.

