**(5) Secondary Aim:** Generate estimates of cost-effectiveness. We will compute within-study costs for CBT, LDX, CBT+LDX and SMART Stage 2 interventions. Repeated assessments will track additional clinician visits and medication use in our RCT as well as outside treatment contacts through the 18-months. SF-12, administered pre- and post-treatments and at follow-ups, will be used to calculate quality-adjusted life years (QALY) following established methods (Revicki et al., 2005) also used in BED studies of cost-effectiveness specifically of LDX (Agh et al., 2016) and CBTgsh (Lynch et al., 2010; Dickerson et al., 2011), as well as for obesity (Tsai et al., 2005; Malone et al., 2005) including obesity medications (Ara et al., 2012), and for similar SMART designs (switching medication for initial non-responders) in depression (Singh et al 2017). We will calculate incremental cost-effectiveness ratios (ICERs) for the various arms; in these ICERs, the numerator will be the incremental medical cost and the denominator will be the incremental effectiveness of the specific treatment compared to CBT. Confidence intervals for the ICERs will be determined using non-parametric bootstrapping. These ICERs will be compared to the two previous BED (Agh et al., 2016; Lynch et al., 2010) analyses and inform subsequent more definitive larger-scale effectiveness studies.

**POWER ANALYSIS:** We calculated our sample size to have at least 80% power at 2-tailed alpha level 0.025 (adjust for 2 outcomes) to detect clinically meaningful effects in Stage 1 for co-primary outcomes (binge eating and weight loss) and Stage 2 for primary outcome (relapse by initial Responders) at 2-tailed level of 0.05 according based on documented effects of the two treatment components (LDX and CBT). In Stage 1, with 180 subjects total (60 per treatment group), accounting for up to 20% dropout, we can detect medium effect sizes ( $d=0.64$ ,  $f=0.32$ ) for the between group comparisons with more than 80% power at two-sided alpha level of 0.025. These effect sizes are smaller than the effect sizes calculated based on data (Telch et al., 1990; [name] et al., 2005; McElroy et al., 2015, McElroy 2016) which ranged  $d=0.69$  to  $d=0.78$  for the comparison of CBT to LDX on binge-eating and was  $d=1.53$  for LDX vs CBT on percent weight loss. Dropout

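### The DSMB's scheduled reports carry no safety data by arm; the reason given fits interim efficacy tests, and the cost falls mainly on the small Stage 2 drug arms

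*Combined protocol and SAP*

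**What the plan says.** The Data and Safety Monitoring Plan explains that projected effects may be too small to detect at an interim look, and continues: "we are not proposing a preliminary analysis of accumulating efficacy and safety data by treatment assignment". The substitute follows at once: "Instead, we propose to submit a twice-yearly report of aggregate data to the DSMB members". Under Measurement and reporting of adverse events, the plan adds: "These data will be collected and examined with blindness to the medication conditions".

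The board nevertheless has power to act on safety. Under Trial Stopping Rules, Limits of Rules: "the DSMB has the authority to stop the trial following any serious adverse event or following reviews of adverse events". There is also an early-warning route: "if adverse events occur in greater magnitude or frequency than expected these will be reported to the DSMB, HIC, and NIH". No expected rate or threshold is given, overall or by arm.

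Group-level review is planned for other data. On retention: "Any differential dropout across blinded study groups and/or higher than expected dropout will be reviewed by the investigators". Baseline differences across blinded groups are to be evaluated yearly (Limits of Assumptions). No section provides for adverse events by arm, coded or unblinded, to reach the DSMB.

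**The concern.** The sentence that rules out by-arm analysis covers efficacy and safety together, but its reason concerns the chance of detecting a treatment effect early. A descriptive safety table tests no efficacy hypothesis and spends no alpha. A board that may stop the trial after reviewing adverse events would ordinarily see whether those events are more frequent in one arm than in its comparators.

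The design makes pooling costly in Stage 2. At that point the trial holds LDX and placebo responders, NB and placebo non-responders, and CBT-only participants who receive no further treatment. A raised event rate on one drug is averaged over all of them. At stake is whether the board can recognise an excess in one small drug arm while there is still time to act on it.

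**Working it through.** **Inputs from the documents**
- Stage 1: "with 180 subjects total (60 per treatment group), accounting for up to 20% dropout" (Power Analysis). So 120 start LDX, alone or with CBT, and 60 receive CBT only.
- Stage 2: 65–70% of the 120 are expected to respond, about 80 people, randomised equally to LDX or placebo. Non-responders go to NB or placebo. CBT-only participants are followed untreated (Research Plan).

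**Inputs assumed here**
- 1:1 allocation to NB and placebo (the ratio is not stated).
- Background and affected-arm event rates.
- A one-sided 5% flag.
- Full cohorts.
- One pooled denominator of 180 (the plan does not say whether the aggregate report is split by stage).

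**1. The plan's own figures**
- Responders: 0.65 × 120 = 78 and 0.70 × 120 = 84, consistent with about 80. After 20% dropout, 80 × 0.8 = 64, or 32 per arm.
- Relapse of 4% against 32%, 32 per arm, two-sided 0.05: exact enumeration of the uncorrected chi-square gives 89.3%, matching the stated 89%.

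The headcounts are therefore sound. The plan states no detection figure for safety.

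**2. Arm sizes and dilution**

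Pooled rate = [n_arm × p1 + (N − n_arm) × p0] / N, so the share of an arm's excess risk that survives pooling is n_arm / N.
- Stage 2 LDX: 80 / 2 = 40; 40/180 = 22% (40/120 = 33% if only re-randomised participants are pooled).
- NB: (120 − 80) / 2 = 20; 20/180 = 11%. With 84 or 78 responders NB is 18 or 21, giving 10–12%. Of the 120 re-randomised it is 20/120 = 17%.
- CBT+LDX alone: 60/180 = 33%.
- Both Stage 1 LDX arms: 120/180 = 67%.

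Example: background 2%, NB 10%. Pooled rate = (20 × 0.10 + 160 × 0.02)/180 = 5.2/180 = 2.9%. Expected events rise from 180 × 0.02 = 3.6 to 5.2, although risk on NB is five times background.

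**3. Chance of a flag**

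Pooled: the smallest total whose binomial tail probability at the background rate is at most 5% (8 or more events of 180 at 2%; 15 or more at 5%), evaluated by exact binomial convolution. By arm: one-sided Fisher test of the affected arm against all other participants.

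| Affected arm | Background to arm rate | Pooled | By arm |
|---|---|---|---|
| NB, 20 of 180 | 2% to 10% | 15% | 35% |
| NB, 20 of 180 | 2% to 20% | 43% | 80% |
| NB, 20 of 180 | 5% to 20% | 22% | 56% |
| Stage 2 LDX, 40 of 180 | 2% to 10% | 37% | 56% |
| Stage 2 LDX, 40 of 180 | 5% to 20% | 54% | 79% |
| CBT+LDX alone, 60 of 180 | 2% to 10% | 61% | 65% |
| Both Stage 1 LDX arms, 120 of 180 | 2% to 10% | 96% | 57% |

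The pooled column assumes the background rate is known, which favours pooling; the plan gives no such rate.

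**4. Sensitivity (2% to 10% on NB)**
- Pooling only the 120 re-randomised: 21% pooled, 30% by arm.
- Half the cohort, 10 of 90: 12% pooled, 17% by arm.
- NB against its own placebo, 20 against 20: 3% by Fisher. A pooled flag over those 40 gives about 43% if the background is known.

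**The case against.** The strongest reply is that the plan has safeguards that do not depend on pooling: serious events go to the NIH and the IRB within 48 hours, each event is attributed, the physician is notified of blood-pressure or heart-rate changes, and the board may meet ad hoc. The aggregate report may also carry other helpful data. This stands in part. A reader might infer that the DSMB is blind to harm or powerless to act, and the documents do not support that: a striking single event could well be noticed. But these routes handle individual events or changes within a person. None is said to give the board event rates by arm, and the early-report trigger has no stated expected rate.

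A second reply is that by-arm tables have little power in small arms, so the plan's reason has some force for safety too. This also stands: at half the cohort the NB gain is 12% to 17%, and NB against its own placebo is nearly uninformative at these rates. It limits what the table can show, but it does not justify withholding it.

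A reader might also infer that pooling hides a general LDX harm in Stage 1. It does not do so materially: two-thirds of the Stage 1 pool is on drug, the pooled flag there is strong if the background is known, and for CBT+LDX alone the two approaches nearly agree. Nor should side-effect discontinuation be averaged over all three Stage 1 arms, because CBT-only participants have no study drug to discontinue. The plan's 9% discontinuation figure comes from a 12-month open-label extension and is not a benchmark for 12 weeks.

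**Conclusion.** The concern holds, centred on Stage 2. The plan excludes safety tabulation by assignment for a reason that mainly concerns efficacy, and nothing else in the documents supplies the comparison. About 89% of an NB-specific excess and 78% of a Stage 2 LDX-specific excess is lost in a pool of 180 (1 − 20/180 and 1 − 40/180). In the NB scenarios tabulated, by-arm display roughly doubles the chance of a flag, from 15–43% to 35–80%, with full cohorts and comparison against all others. The gain is smaller at interim.

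The dilution shares rest on the plan's headcounts, 1:1 NB allocation and a denominator of 180. The detection figures rest in addition on assumed event rates and an assumed 5% flag. The exclusion is a disclosed design choice, and it does not affect the validity of the efficacy analyses. The sponsor should change it because the correction is cheap and the board already holds the authority that the table would inform.

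**What to change.** In the Data and Safety Monitoring Plan, keep the statement that there will be no interim efficacy analysis and delete *and safety* from it. Add a closed DSMB table, twice a year, with these features:
- **Content:** adverse events, serious adverse events, blood pressure and heart rate, liver tests, and side-effect discontinuations, the last among medicated participants only.
- **Layout:** by coded arm, with Stage 2 shown separately for responders and non-responders.
- **Preparation:** from the pharmacy's assignment codes, by someone not involved in treatment or assessment. The study coordinator and PI, who now generate and sign the report, keep the aggregate open version.
- **Status:** descriptive, with no test and no alpha spent; the plan should say that the NB comparison will not be well powered.

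In the same edit, reconcile the report form, which lists all adverse events, with the description of the aggregate report, which names only serious ones.

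The cost is one extra table set twice a year, an independent preparer, and a small risk that the board infers which code is which. The study team's blind is unaffected if the report stays closed.

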**Measurement and reporting of adverse events.**

Adverse event data will be collected on an on-going basis. These data will be collected and examined with blindness to the medication conditions. Adverse events data will be reviewed by the PI, co-investigators, and the safety officer throughout this trial (see Table below). A summary of adverse events will be provided to the Yale IRB yearly during the annual renewal review process. Any serious or unanticipated adverse events will be reported to the NIH and to the Yale IRB within 48 hours.

The frequency of data review is summarized in the following table:

Table	Data type	Frequency of Review by PIs and Research Team	Frequency of Review by PI and DSMB
Table 1	Subject accrual	Monthly	Twice Yearly
Table 2	Treatment completion rates (retention/attrition)	Twice Yearly	Twice Yearly
Table 3	Adverse and serious adverse event rates	Twice Yearly	Twice Yearly
Table 4	Checklist for DSMB	NA	Twice Yearly

**Attribution of Adverse Events:**

Adverse events will be monitored for each subject participating in the study and attributed to the study procedures by the investigators according to the following categories:

- a) Definite: Adverse event is clearly related to the investigational procedure/agent.
- b) Probable: Adverse event is likely related to the investigational procedure/agent.
- c) Possible: Adverse event may be related to the investigational procedure/agent.
- d) Unlikely: Adverse event is likely not to be related to the investigational procedure/agent.
- e) Unrelated: Adverse event is clearly not related to the procedure/investigational agent.

**Plan for Grading Adverse Events:**

The following scale will be used in grading the severity of adverse events noted during the study:

1. Mild adverse event
2. Moderate adverse event
3. Severe adverse event

**Plan for Determining Seriousness of Adverse Events:**

**Serious Adverse Events:** In addition to grading the adverse event, the PI will determine whether the adverse event meets the criteria for a Serious Adverse Event (SAE). An adverse event is considered serious if it results in any of the following outcomes:

1. Death;

2. A life-threatening experience in-patient hospitalization or prolongation of existing hospitalization;
3. A persistent or significant disability or incapacity;
4. A congenital anomaly or birth defect; OR
5. Any other adverse event that, based upon appropriate medical judgment, may jeopardize the subject's health and may require medical or surgical intervention to prevent one of the other outcomes listed in this definition.

An adverse event may be graded as severe but still not meet the criteria for a Serious Adverse Event. Similarly, an adverse event may be graded as moderate but still meet the criteria for an SAE. It is important for the PI to consider the grade of the event as well as its "seriousness" when determining whether reporting to the IRB is necessary.

Plan for events to the Yale IRB that are unexpected AND related AND involve risk of harm to subjects or others:

The PIs will report any incident, experience, or outcome that meets all three of these conditions to the IRB immediately:

1. Unexpected (in nature, specificity, severity, or frequency); given (a) the research procedures described in the protocol-related documents, such as the IRB-approved protocol and informed consent document and (b) the characteristics of the subject population being studied; AND
2. Related or possibly related to participation in the research (possibly related means there is a reasonable possibility that the incident, experience, or outcome may have been caused by the procedures involved in the research); AND
3. Suggests that the research places participants or others at greater risk of harm (physical, psychological, economic, legal, or social) than previously known or recognized.

Unanticipated Problems Involving Risks to Subjects or Others (UPIRSOs) may be medical or non-medical in nature, and include – but are not limited to – *serious, unexpected, and related adverse events* and *unanticipated adverse device effects*. Adverse events are reportable to the IRB as UPIRSOs only if they meet all 3 criteria listed above.

These UPIRSOs/SAEs will be reported to the IRB in accordance with IRB Policy 710, using the appropriate forms found on the website. All related events involving risk but not meeting the prompt reporting requirements described in IRB Policy 710 should be reported to the IRB in summary form at the time of continuing review and/or a current DSMB report. If appropriate, such summary may be a simple brief statement that events have occurred at the expected frequency and level of severity as previously documented.

Plan for reporting adverse events to co-investigators on the study, as appropriate the protocol's research monitors, e.g., study sponsors, funding and regulatory agencies, and regulatory and decision-making bodies:  
For the current study, the following individuals, funding, and/or regulatory agencies will be notified:

- i. All Co-Investigators listed on the protocol
- ii. National Institutes of Health

The investigators will conduct a review of all adverse events upon completion of every study subject. The investigators will evaluate the frequency and severity of the adverse events and determine if modifications to the protocol or consent form are required.

Procedures for providing follow up care:

Medical monitoring will occur at all clinic and follow up visits and medical care will be provided if warranted. If a study participant experiences any psychiatric symptoms or distress (e.g., depressive symptoms or suicidality) at any stage of study participation he/she will receive short-term treatment and support from the study treatment team (including psychologists and a psychiatrist) and will be connected to a local emergency department (e.g., the Crisis Intervention Unit at Yale-New Haven Hospital) and his/her physician or therapist for ongoing care.

Measurement and reporting of subject accrual, adherence to inclusion/exclusion criteria.

Review of the rate of subject accrual and adherence to inclusion/exclusion criteria will occur regularly by the PI and co-Investigators and yearly by the safety officer. These reviews will help to assure that participants meet eligibility criteria and ethnic diversity goals outlined in the grant proposal.

Measurement and reporting of participant treatment completion rates.

Participation rates (retention and attrition) will be reviewed on an ongoing basis by the PIs and co-investigators to identify any potential problems, and formally by the PIs and DSMB twice-yearly. Any differential dropout across blinded study groups and/or higher than expected dropout will be reviewed by the investigators to determine whether any problems are present and what, if any, corrective action needs to be taken.

During the reviews, if the DSMB has concerns about whether attrition has reached a level that might inhibit the ability of the study to address its primary aims, they will suggest a meeting to discuss methods for improving subject retention. Previous pharmacotherapy studies for BED (with comparable time frames for pharmacotherapy) have reported attrition rates between 20% and 38%. Studies of NB for obesity treatment reported attrition of 30% to 45%. Thus, "trigger points" for review and discussion by principal investigator and research staff will be: 35% ("low alert"), 40% ("mid alert"), 45% ("high alert"), 50% ("extreme alert"). With early alerts to problems, action would be taken to avoid higher level alerts; if a higher level alert should arise, more drastic actions would be taken.

Trial Stopping Rules

Given that this study is deemed greater than minimal risk to human subjects, it is more likely that attrition or difficulty in recruiting adequate numbers of participants will require stopping the trial than would excess adverse events. However, as outlined, adverse events will be monitored in all participants, and the safety officer, together with the PI, will alert the Yale IRB and the NIH if a larger (or more serious) than reasonably expected adverse event rate should occur. Other potential issues relating to stopping rules for this trial include:

1. New Information

It is unlikely that any new information will become available during this trial that would necessitate stopping the trial. If new safety data (i.e., pertaining to short-term use of the study medication) become available, this will be evaluated.

2. Limits of Assumptions

It is possible that baseline differences between the treatment conditions, excessive attrition, and/or missing data could limit the value of data analysis. Baseline differences across blinded treatment groups, if present, will be evaluated yearly and considered in relation to potential effects on the power to detect differences in the primary outcomes. If these effects were to develop and be sizeable, alterations to the

randomization schedule would be considered. Any plans to alter the randomization scheme would be communicated to the NIH.

The following actions would be taken at each level of alert:

- (1) Low-level alert = Review of potential problems by PI.
- (2) Mid-level alert = Meeting with co-investigators to discuss approaches to minimize further losses to follow-up/dropouts.
- (3) High-level alert = Meeting with co-investigators to determine further alterations of study protocol to complete the study with no further losses.
- (4) Extreme-level alert = In the unlikely event of a 50% dropout rate prior to the mid-study time point, discontinuing the trial would be considered.

